measures taken during outpatient therapy on BAC (B), and post-outpatient treatment (A).

Subject Recruitment

20 elderly 5 days or more post-CVA admitted to Kessler Institute for Rehabilitation/Kessler Foundation) for inpatient rehabilitation will be recruited. Subjects will be pre-screened through a standardized questionnaire and MoCA screening. We expect to screen at least 70 potential subjects, also trying to determine candidates who will continue outpatient rehabilitation at Kessler Foundation. Those who met inclusion criteria will be consented by [name] MD or [name] (Co-Investigators). The 20 recruited subjects will subsequently be randomised equally into an experimental group (n=10) and a control group (n=10).

We will also recruit the 20 caregivers of the experimental and control subjects. The caregivers will provide feedback on the subjects during the outpatient component of their therapy, every 4 weeks. We will be looking for changes in independence in activities of daily living, cognition and mood that the caregivers will report, as well as self-reported outcomes by the subjects. The feedback will be using the Stroke Impact Scale [Duncan et al. 2002] and the Upper Extremity Functional Index (UEFI) [Stratford 2001] standardized questionnaires, as well as free form communication with researchers.

Subject standardised evaluations for control study on early sub-acute post stroke

Both experimental and control groups will undergo standardised evaluations for motor function/impairment, cognition and emotive states. All subjects will be evaluated before, and after their in-patient rehabilitation. Those patients who transition to home rehabilitation will be evaluated again before commencing outpatient rehabilitation, while those who transition directly to outpatient rehabilitation will not. All subjects will be evaluated again at the completion of their outpatient therapy. All clinical evaluations of the control study subjects will be performed at the Kessler Kessler Foundation.

OT evaluations

An occupational therapist blinded to the treatment allocation will evaluate for motor impairment and function of both UEs. These evaluations are the following:

- Fugl Meyer Assessment (FMA)
- Jebsen test of hand function [Jebsen 1969]
- active range of shoulder, elbow and finger movement (goniometer)
- shoulder strength (wrist weights)
- range of forearm pronation/supination
- grasp strength (dynamometer)

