- pinch strength (pinch-meter)bimanual activities (Chedoke Inventory -9) [Barreca 2000]. The need to evaluate both UEs stems from the nature of BAC bimanual training and from our inclusion of subjects who may be bilaterally affected by their first CVA.

Emotional & Neuropsychological evaluations

- The neuropsychologist will perform the cognitive/emotive evaluations. We will assess
- emotive state (via the Beck Depression Inventory II)
 - verbal and visual attention (with the Neuropsychological Assessment Battery NAB)
 - processing speed (with the Trail Making Test A [Heaton 1991] - TMT)
 - verbal and visual learning and memory (with the Hopkins Verbal Learning Test, Revised (HVLTR) [Brandt 2001])
 - Brief Visuo-spatial Memory Test, Revised (BVMT-R) [Benedict 1997])
 - executive function with the Trail Making Test B (TMT-B) and the NAB Executive Functioning Module.

The initial evaluations will serve as baseline for all participants. Subsequent to the inpatient VR training, all participants will be evaluated again for cognitive and emotive state for indication of clinical benefit. Subjects who transition to home will be evaluated again at the start of their outpatient rehabilitation. All subjects will be evaluated again for cognitive and emotive state at the end of their outpatient therapy. For subjects who skip home rehabilitation and transition directly to outpatient training, the measures at discharged from inpatient rehabilitation will be considered as baseline for start of outpatient training. To minimize test learning effects we will use alternate test forms for NAB tests, as well as reliable change formulas for all other forms [Jacobsen and Truax, 1991].

Inpatient and outpatient experimental therapy for the control study at Kessler Foundation

All subjects, regardless of group randomisation, will continue their standard of care rehabilitation (physical therapy, occupational therapy, speech and language therapy and cognitive training). All subjects, regardless of randomization, will have the same duration of therapy. Specifically, subjects randomised in the control group will have an added duration of standard of care rehabilitation equal to the experimental group training duration on the BAC.

Experimental group

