10 subjects in the experimental group will be trained on the BAC system in addition to their standard of care intervention. Sessions will consist of a series of non-repeating custom and adaptable integrative games played while sitting at the robotic table. During the in-patient portion of the experimental therapy they will perform sessions every other day, for up to 3 weeks (12 sessions total). When transitioning to outpatient therapy, they will perform 2 to 3 sessions a week for 2 to 3 months.

Each experimental session will start with baseline measures of supported arm reach, pronation/supination range, finger extension and grasp strength. These measures will be done for the more affected arm during the initial 4 sessions, and for both arms thereafter, since therapy will progress to bimanual mode. The length of each session will increase with the progression of therapy, from 15 minutes in the first in-patient therapy session, to 30 minutes during the last in-patient session. Then during outpatient therapy portion, sessions will commence at 30 minutes duration and will progress to 45 minutes of actual game play.

The tilting angle of the robotic table will be used to modulate gravity loading on (typically) weak arms. If the subject is low-functioning the table may be tilted downwards to assist movement away from the trunk. Conversely, as the subject gets stronger, the table will be tilted upwards so to increase gravity loading. We plan on keeping the table flat during the inpatient sub-acute training and envisage this upwards tilting to occur in the outpatient component of the therapy.

Apart from lengthening the sessions and increasing gravity loading through robotic table tilting, we will increase session difficulty by incrementing the difficulty level of individual games. For example we may increase the number of face-down cards to be paired during the *Card Island* game (which trains short term visual and auditory memory), or increase the speed of the ball during *Breakout 3D* game (which trains hand-eye coordination, focusing, and dual tasking). In the outpatient portion, when attempting to lift the arm off the table, the weight of the forearm support will increase training difficulty further.

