In the motor domain the session will train endurance (by increasing the length of training), strength (by modulating gravity loading and lifting arm off table), motor control (by requiring patients to follow prescribed paths), and movement speed (by inducing more arm repetitions per minute).

In the cognitive domain the cognitive load will gradually be increased by moving from uni-manual play (need to control only one avatar) to bimanual play (simultaneous control of two avatars). This will train split attention, task sequencing and dual tasking, something problematic for the elderly.

Control group

10 subjects in the control group will receive their standard of care intervention during inpatient rehabilitation post CVA. To this we will add an equal duration of standard of care to the experimental therapy (progressing from 15 minutes/session in sessions 1-4 to 30 minutes during the last inpatient session). In the outpatient period they will have an added duration of customary therapy. The added therapy will progress from 30 minutes/session at start of outpatient therapy to 45 minutes/session at the end, matching the experimental group training duration on the BAC.

Control study Outcomes

Primary outcomes

The primary outcomes for both groups will be those outlines in the Feasibility Study component of the project. The main motor outcome measure will be the FMA UE score, and success will be a group average score increase of 10 points or more, compared to baseline. The main outcome for the cognitive domain will be executive function improvement measured by Trail Making Test B (TMT-B) and the NAB Executive Functioning Module.

Secondary outcomes

The secondary outcomes for both groups will be those outlined in the Feasibility Study component of the project,

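### The randomised trial's motor success rule is a within-group 10-point gain that ignores the control arm, so it can be met when BAC has no effect

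*Protocol*

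**What the plan says.** The rule stands in the protocol's section on the randomised study, under Control study Outcomes, Primary outcomes: "success will be a group average score increase of 10 points or more, compared to baseline". The same sentence appears under the feasibility study's primary outcomes, and the randomised section says where it came from: "The primary outcomes for both groups will be those outlines in the Feasibility Study component of the project".

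The two designs differ. The feasibility study is a pre/post (ABA) study of 6 inpatients without controls. The Kessler study randomises 20 patients equally, 10 to BAC plus standard care and 10 to standard care plus an equal added amount of standard care: "All subjects, regardless of randomization, will have the same duration of therapy". The Control group section repeats this for the outpatient period, with added therapy "matching the experimental group training duration on the BAC".

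On timing, "All subjects will be evaluated before, and after their in-patient rehabilitation", and "All subjects will be evaluated again at the completion of their outpatient therapy". Patients who go home first have a further assessment before outpatient therapy starts. On baseline, the protocol says "The initial evaluations will serve as baseline for all participants".

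Two other places bear on the comparison. The additional outcome at the end of Control study Outcomes is a set of recovery curves meant to distinguish natural recovery from the effect of BAC training. Data Analysis and Data Monitoring plans a repeated measures ANOVA, described as a comparison of pre-training with post-training results.

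**The concern.** A threshold on the change within a group may serve as a benchmark in a single-arm pilot. In a randomised trial the question is whether the BAC arm does better than the control arm, and this rule never asks it.

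The protocol itself supplies the reasons why a within-group gain cannot answer that question. The Background describes the early sub-acute phase as one of heightened plasticity. The outcomes section expects some gain from natural recovery. Controls receive extra therapy for the same time. The stated aim is the benefit of BAC on top of conventional rehabilitation. Either arm, or both, could therefore gain 10 points for reasons unrelated to BAC.

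The rule is also incomplete as a decision. It applies to both groups without saying which must pass, and it does not say whether the gain is read after inpatient or after outpatient therapy. If both arms pass, or only the control arm does, the protocol does not say what is concluded about BAC.

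**Working it through.** The protocol states no SD, expected gain, alpha, power or sample-size calculation, so it has no figure to reproduce. The check asks how the rule behaves when BAC does nothing.

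**Inputs from the protocol.** Threshold 10 points; n = 10 per arm.

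**Assumptions.** SD of FMA-UE change 7 to 10; the same true mean gain *m* in both arms (zero BAC effect); independent arms; approximately normal means.

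**Chance that one arm passes.** p = 1 − Φ((10 − m) / (SD/√10)). The standard error of a group mean is 7/√10 = 2.21 or 10/√10 = 3.16. For m = 8, z = 2/2.21 = 0.90 gives p = 0.183, and z = 2/3.16 = 0.63 gives p = 0.264. Both arms pass with probability p², and only the control arm passes with probability p(1 − p).

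| Common true gain | BAC arm passes (SD 7; SD 10) | Both pass | Only control passes |
|---|---|---|---|
| 3 | 0.001; 0.013 | <0.001; <0.001 | 0.001; 0.013 |
| 5 | 0.012; 0.057 | <0.001; 0.003 | 0.012; 0.054 |
| 8 | 0.183; 0.264 | 0.034; 0.069 | 0.150; 0.194 |
| 10 | 0.500; 0.500 | 0.250; 0.250 | 0.250; 0.250 |
| 12 | 0.817; 0.736 | 0.667; 0.542 | 0.150; 0.194 |

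The pass rate is set by recovery that has nothing to do with BAC. The rule also errs in the other direction: if controls truly gain 3 and BAC patients 8, a real 5-point advantage, the BAC arm passes only 18–26% of the time (the m = 8 row).

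**Between-arm alternative.** If success requires a two-sided 95% CI for BAC minus control to exclude zero in favour of BAC, false success is 2.5% whatever the common gain. For an unadjusted two-sample comparison on 18 degrees of freedom:

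- CI half-width = 2.101 × SD × √(2/10), which is 6.58 (SD 7) or 9.40 (SD 10) points.
- Power for a true 6-point benefit (noncentral t): 0.442 (SD 7) or 0.245 (SD 10).
- True difference needed for 80% power: 9.27 (SD 7) or 13.25 (SD 10) points.

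Baseline adjustment may improve on these figures; by how much cannot be said from the protocol.

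**The case against.** The strongest reply is that the protocol does intend a comparison. The recovery curves are meant to separate natural recovery from training, a repeated measures ANOVA can carry a group-by-time term, and a SAP that is not shown may specify one. The ANOVA paragraph is general and also covers the single-arm components, so its pre/post wording is weak evidence that group is left out for the randomised study. This limits the point to the success rule: it would be wrong to say the trial never uses its controls. It does not rescue the rule. The curves are visual and listed as an additional outcome, neither the curves nor the ANOVA is tied to success, and the protocol itself fixes the success definition. A between-group test in a SAP would leave two competing criteria.

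The probabilities rest on assumed gains close to the threshold. That is fair: at a common gain of 3 to 5 points the BAC arm passes only about 0.1–6% of the time. The documents support the statement that the rule can be met without a BAC effect, not that it often will be.

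The baseline sentence sits under the neuropsychological evaluations, and discharge measures serve as a second baseline for outpatient training in patients who transfer directly. Reading the initial evaluation as the FMA-UE baseline is therefore the natural reading, though not an explicit one.

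Finally, this is a 20-patient study seeking early indications of benefit. That argues for an estimate with its interval rather than heavy reliance on a significance test. It does not justify a criterion that cannot tell BAC from recovery.

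**Conclusion.** The concern holds, and the rule must be corrected. As written, the primary motor criterion of the only randomised component can be met by natural recovery and extra therapy time alone, which is what the time-matched control arm was designed to rule out. That conclusion follows from the wording and needs no assumption.

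How often it would happen does need assumptions. With 10 per arm, SD of change 7 to 10 and no BAC effect, false success in the BAC arm ranges from about 1–6% at a common gain of 5 points to 74–82% at 12 points. At 12 points both arms would pass together in 54–67% of trials, an outcome for which the protocol gives no interpretation.

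**What to change.** - **Control study Outcomes, Primary outcomes:** define the primary motor result as the BAC minus control difference in FMA-UE at one named post-treatment visit, adjusted for the initial pre-inpatient FMA-UE, with a two-sided 95% CI. Success means that the interval excludes zero in favour of BAC. The proposed visit is the end of outpatient therapy, with the end of inpatient therapy as secondary. State that the pre-inpatient assessment is the FMA-UE baseline and, since both limbs are assessed, which limb's score is analysed.
- **Data Analysis and Data Monitoring:** add one sentence naming this contrast as the primary analysis of the randomised study.
- **10-point gain:** keep it as a descriptive benchmark for each arm.
- **Other outcomes:** report the 5-point BDI-II criterion among the secondary outcomes as a between-group difference too. The cognitive primary outcome would need its own contrast; the 2.5% figure covers the motor result only.
- **Feasibility study:** leave its rule unchanged.

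The cost is a few sentences of wording; the assessments are already scheduled. The drawback is low power at 10 per arm: 25–44% for a true 6-point benefit before any gain from adjustment. The result should therefore be presented mainly as an estimate with its interval. The change controls false success but does not by itself make the trial more sensitive.

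The choice of visit also has a price. In the outpatient phase "they will perform 2 to 3 sessions a week for 2 to 3 months", so its end is not one fixed time. The end of inpatient therapy would be more uniform but would leave out the outpatient training.

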The first BAC system will be installed at PowerBack and 6 participants 5 to 10 days post CVA admitted to inpatient rehabilitation will be recruited. They will train for up to 3 weeks, every other day, totalling up to 12 rehabilitation session playing a series of integrative exercises. Each session will start with a baseline for arm reach in the horizontal and vertical plane, pronation/supination range, as well as grasp strength and finger extension. These baselines will be used to adapt each game to an individual participant's motor impairment level in a given day, making the games winnable. Games

will produce congratulatory feedback, designed to maximize motivation, giving the subjects a feeling of control over their therapy and of accomplishment.

To combat boredom, new games will be added, such that the number of available games will progress from 4 games for sessions 1-4 to 6 games for sessions 5-8, and 8 games for sessions 9-12. The characteristics of each game will change from week to week (for example later-stage games will use dual-tasking involving moving and grasping simultaneously). Subjects will have a choice of games to play from among those available and will know the level they had achieved in a particular game.

The VR training will progress from 15 minutes/session of actual play (sessions 1-4), to 20 minutes (sessions 5-8) to 30 minutes (sessions 9-12). The BAC will be used in uni-manual mode providing training to the affected UE in sessions 1-4, and in bimanual mode for sessions 5-12. Furthermore, grasp and shoulder training will progress from no grasping required in sessions 1-4, to momentary grasping needed to play in sessions 5-12. Towards the end of training each session should induce >600 repetitions/arm, an amount consistent with inducing brain plasticity [Nudo 1997]. Subjects will play while supported by the BAC table in horizontal position. At the discretion of the therapist in the room, if moderate to mildly impaired participants tolerate, the table may be tilted up to 10 degrees.

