- bimanual training to improve CAHAI 9 scores (by at least 6 points), reflecting more ADL independence in tasks that are requiring both arms. The progression in ADL independence will be indicative of transfer to function.
- Other secondary outcomes will be changes in therapeutic game scores,
- change in game duration (indicative of reduction in task completion time)
- change in play intensity (number of arm movement repetitions/minute);
- participants' subjective evaluation scores for ease of use of the BAC, and overall system rating.

In the cognitive domain, secondary outcomes will be:

- improved focus,
- better verbal and visual memory.

In the emotional domain, we will evaluate the depression scores as measured by the Becks Depression Inventory II standardized test. We will consider success an average group reduction of 5 points in the severity of depression.

Pilot Feasibility Study for BrightBrainer use by individuals with PD (BCI/CCIT site)

This will be an ABA protocol. Measures will be taken pre- outpatient therapy (A), during outpatient experimental therapy on BrightBrainer (B), and post inpatient therapy (A).

Subject Recruitment

[name] OT will reach out to PD support groups in NJ to publicize the pilot. She will use the publicity flier developed for this purpose. Those interested will be consented at CCIT.

Subject standardised evaluations for pilot feasibility study on individuals with PD.

- the Canadian Occupational Performance Measure (Law et al., 2005)
- the Upper Extremity (UE) dual task function test. UE dual task function test involves repeated upper extremity elbow flexion with a gyroscope to measure repetitions and angular velocity with an added cognitive task such as counting backwards by seven or counting months of the year backwards (Toosizadeh et al., 2016)
- Timed Up and Go Cognitive (Shumway-Cook, Brauer, & Woollacott, 2000),
- cognitive measures of Trail making test (Reitan & Wolfson, 1994)

- Stroop test (Hsieh, Chen, Wang, & Lai, 2008).
- Upper extremity specific measures of Nine Hole Peg Test (Mathiowetz & Kashman, 1985)
- Modified functional reach test (Smithson, Morris, & Iansek, 1998),
- Parkinson's Disease Activities of Daily Living Scale (Hobson, Edwards, & Meara, 2001) and

Movement Disorder Society Unified Parkinson's Disease Rating Scale (Goetz et al., 2007)

Outpatient experimental therapy for individuals with PD

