Two subjects will do 12 sessions over 4 weeks at CCIT, playing the same therapeutic games previously described. Session duration and progression will be same. An additional variable will be arm tremor (in terms of magnitude and frequency).

Two new baselines will be added, to determine tremor for each arm and for the index finger. The baselines will be done before each session and will use the BrightBrainer VIVE game controllers. The frequency of data sampling from these controllers is sufficient to measure the hand and index finger tremor and will inform game sensitivity parameters.

PD pilot study Outcomes

Primary outcomes

The primary outcomes will include Canadian Occupational Performance Measure (Law et al., 2005) and Upper Extremity (UE) dual task function test. UE dual task function test involves repeated upper extremity elbow flexion with a gyroscope to measure repetitions and angular velocity with an added cognitive task such as counting backwards by seven or counting months of the year backwards (Toosizadeh et al., 2016)

Secondary outcomes

The secondary outcomes will include another dual task measure of lower extremity Timed Up and Go Cognitive (Shumway-Cook, Brauer, & Woollacott, 2000), cognitive measures of Trail making test (Reitan & Wolfson, 1994) and Stroop test (Hsieh, Chen, Wang, & Lai, 2008). Upper extremity specific measures of Nine Hole Peg Test (Mathiowetz & Kashman, 1985) and Modified functional reach test (Smithson, Morris, & Iansek, 1998), and two PD specific scales of Parkinson's Disease Activities of Daily Living Scale (Hobson, Edwards, & Meara, 2001) and Movement Disorder Society Unified Parkinson's Disease Rating Scale (Goetz et al., 2007)

Other secondary outcomes will be changes in therapeutic game scores, change in game duration (indicative of reduction in task completion time) and change in play intensity (number of arm movement repetitions/minute). Another secondary outcome will be subjective evaluation scores for ease of use of the BrightBrainer, and overall system rating using System Usability Scale.

Randomized control study protocol (Kessler Foundation IRB Oversight)

This will be an ABA (A)BA protocol. Measures will be taken pre- inpatient therapy (A), during inpatient experimental therapy on BAC (B), , post inpatient therapy (A). After discharge, measurements will again be taken pre- outpatient therapy (A) if outpatient therapy is not started immediately after inpatient therapy. All subjects will have

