In the motor impairment domain, secondary outcomes will be increased arm range in pronation/supination (based on new games we developed), grasp strength increase, finger extension range increase, and increase in UEFI. We expect bimanual training to improve CAHAI 9 scores (by at least 6 points), reflecting more ADL independence in tasks that are requiring both arms. The progression in ADL independence will be indicative of transfer to function. Other secondary outcomes will be changes in therapeutic game scores, change in game duration (indicative of reduction in task completion time) and change in play intensity (number of arm movement repetitions/minute). Another secondary outcome will be subjective evaluation scores for ease of use of the BAC, and overall system rating.

In the cognitive domain, we also foresee the subjects will have improved focus, better verbal and visual memory. In the emotional domain, we will evaluate the depression scores as measured by the Becks Depression Inventory II standardized test. We will consider success and average group reduction of 5 points in the severity of depression.

In addition there will be supplementary secondary outcomes:

- a) Scores obtained on the Stroke Impact Scale (Version 3);
- b) feedback from the subjects during the outpatient component of therapy (only for intervention group);
- c) feedback obtained from caregivers during outpatient therapy. The caregivers for subjects in either experimental or control groups will use the same feedback forms and provide feedback at the same time points.

An additional important outcome will be the rate of motor recovery as visualized by the curves of evaluation variables obtained pre-, and post inpatient therapy, then pre-, and post- outpatient therapy. These will provide indication on the envisaged benefits from the use of the experimental device and elucidate what gains are due to natural recovery and what gains may be attributes to training on the BAC.

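### Change in game duration is read as faster task completion, although the protocol changes the task during training

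*Protocol*

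**What the plan says.** Game duration appears as a secondary outcome with the same gloss in three places of the Protocol. Outcomes of feasibility study has "change in game duration (indicative of reduction in task completion time". PD pilot study Outcomes and Control study Outcomes both have "change in game duration (indicative of reduction in task completion time) and change in play intensity (number of arm movement repetitions/minute".

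The training sections describe what participants play:

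- **Feasibility study** (Inpatient experimental therapy for the feasibility study). On mode: "The BAC will be used in uni-manual mode providing training to the affected UE in sessions 1-4, and in bimanual mode for sessions 5-12". On grasp and shoulder training, the progression is "from no grasping required in sessions 1-4, to momentary grasping needed to play in sessions 5-12". On content: "The characteristics of each game will change from week to week". Each session opens with baselines for reach, forearm rotation, grasp and finger extension, and these adapt each game to the participant's impairment on that day. The table is horizontal, with an optional tilt of up to 10 degrees at the therapist's discretion.
- **Parkinson's pilot** (Outpatient experimental therapy for individuals with PD). Two subjects do 12 sessions, "playing the same therapeutic games previously described. Session duration and progression will be same". Tremor baselines taken before each session "will inform game sensitivity parameters". No table tilt or forearm load is described.
- **RCT** (Experimental group). The difficulty level of individual games will be raised; more cards to pair and a faster ball are given as examples. Play progresses to two-arm mode. The table is planned to stay flat for inpatients, and upward tilt and forearm-support load belong to the outpatient part.
- **General** (Protection Against Risks). Difficulty is set automatically from earlier performance and participants choose their games. For post-stroke participants, difficulty may be lowered temporarily.

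**The concern.** Duration measures speed only when the thing being timed is fixed. Here the plan alters the thing being timed, partly in response to the participant's own performance, and still states in advance what a change in duration means. Someone who follows the text as written could report a longer game as no benefit in a subject who has improved and been moved up a level. Equally, a shorter game could be reported as benefit in a subject whose level was eased. At stake is the interpretation of one listed secondary outcome in three components.

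**Working it through.** The protocol states no figure, target or test for game duration, so there is nothing to reproduce. The check is whether the gloss is compatible with the training plan, followed by a small illustration.

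**Step 1: what the gloss needs.** For a fall in duration to indicate faster completion, the early and late plays must share the game, its level, the number of arms used, the grasp demand, the loading and any scaling to baseline.

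**Step 2: which of these stay fixed.**

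| Setting | Feasibility study | Parkinson's pilot | RCT |
|---|---|---|---|
| Difficulty or content | changes weekly; set from past performance | same games and progression | incremented; set from past performance |
| One or two arms | changes after session 4 | same progression | progresses to two arms |
| Grasp demand | added from session 5 | same progression | not specified by session |
| Rescaling to session baseline | every session | tremor baselines feed sensitivity settings | sessions open with baselines; games described as adaptable |
| Tilt or forearm load | optional tilt, up to 10 degrees | none described | flat for inpatients; upward tilt and load envisaged for outpatients |
| Choice of game | participant's | participant's | participant's |

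In the feasibility study, sessions 1-4 are one-arm without grasp and sessions 5-12 are two-arm with grasp. No play in the first block therefore shares both settings with any later play. No component holds the task fixed across training.

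**Step 3: direction (illustration; the values of k are assumed).** Let duration be D = n × t, where n is the number of items in a game and t is the time per item. If n is multiplied by k and t by r, the new duration divided by the old is k × r. Duration falls only if r < 1/k, that is, if time per item falls by more than 1 − 1/k:

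- k = 1.25: 1 − 1/1.25 = 20%
- k = 1.5: 1 − 1/1.5 = 33%
- k = 2.0: 1 − 1/2.0 = 50%

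A subject whose time per item improves by less than these amounts shows a longer game. Conversely, if the k = 1.25 step is undone, n is multiplied by 1/1.25 = 0.8. With r = 1, duration then falls by 20% with no gain in speed. A faster ball has no clear sign, since the system sets part of the pace. The distortion can therefore run either way, and the document gives nothing from which to fix it.

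**Step 4: what depends on the outcome.** The success criteria in the outcome sections concern FMA, CAHAI 9 and depression scores. The ANOVA in Data Analysis and Data Monitoring compares conventional evaluations before and after training. None of these uses game duration.

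**The case against.** The strongest reply is that this is analysis detail. The protocol names an outcome and adds a hedged gloss. It does not say that durations will be compared raw, pooled across games or compared across levels, and an SAP could restrict the comparison to like-for-like plays. That much stands: the gloss does not exclude matching, so this is not a strict contradiction, and leaving the comparison rule to an SAP would be no fault. What does not stand is that nothing has been fixed. The protocol itself attaches a direction and a meaning, in three places and without any condition, beside a training plan that removes the condition the meaning needs.

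Two limits on scope are also correct. In the RCT, a reader might infer that tilt and forearm load confound the whole course. They do not, because the table is planned to stay flat for inpatients; the inpatient problem comes from difficulty and mode alone. The temporary lowering of difficulty is stated for post-stroke participants and should not be carried over to the Parkinson's pilot.

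A reader might also try to size the problem from the feasibility schedule of "4 games for sessions 1-4 to 6 games for sessions 5-8, and 8 games for sessions 9-12". Those counts show which games are available, not which plays are comparable, because each game's content also changes weekly. They say nothing about the RCT.

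**Conclusion.** The point holds as a matter of interpretation. Change in game duration across sessions mixes ability with task settings in an unknown direction, so it cannot by itself show faster task completion. This rests on the training being delivered as described; it needs no assumption about effect size or variance. The matter is minor: a secondary outcome with no threshold or test.

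Two stronger readings are not supported. One is that the outcome is biased towards benefit: the planned changes can lengthen or shorten a game, so no sign can be claimed. The other is that the trial's conclusions on motor or executive function are at risk: they rest on standardised evaluations that do not use game data. The RCT text that assigns the secondary outcomes to both groups, and the design sentence that gives all subjects measures during outpatient BAC therapy, raise a separate wording question about who plays on the BAC. They are not part of this point.

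**What to change.** In the secondary-outcome lists for the feasibility study, the Parkinson's pilot and the RCT, delete the parenthesis after game duration. Report duration descriptively together with the difficulty level reached.

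Keep the speed interpretation only for within-subject plays of the same game at the same logged level, arm mode, grasp demand and baseline or sensitivity scaling, and at the same tilt where the BAC table is used. Where no such plays exist, make no statement about speed. Training itself need not change.

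Deleting the parenthesis costs only wording. The matched comparison costs a little programming and has three drawbacks:

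- It needs the settings stored with each play. The feasibility section says only that game performance data go to the remote database.
- Matched plays will be few, because games are added, content changes and participants choose.
- Because level follows past performance, matched plays over-represent participants and games that progressed more slowly. This is why the level reached must be shown alongside.

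The RCT section also describes its sessions as a series of non-repeating games. If that means across sessions, the RCT has no matched plays and deletion alone is the right course there.
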